Consensus Auditory-Perceptual Evaluation of Voice (CAPE-V) was used for the auditoryperceptual evaluation of the children's voices (Kempster et al., 2009). This tool is designed to describe the severity of dysphonia by rating six parameters (overall severity, roughness, breathiness, strain, pitch, and loudness) on a visual-analog scale from 0 to 100, where 0 is considered within normal limits. The tool was supplemented by two additional visual-analog scales to measure asthenia and instability (Meerschman et al., 2022). Two experienced voice therapists ([name] and [name]) independently and blindly rated all the pseudonymized samples in a random order.

Afterwards, they relistened to the samples together to compare their individual evaluations and to reach a consensus. The samples consisted of the sustained vowel [a:] and the full text "Papa and Marloes," which were also used to determine the AVQI. The raters were allowed to listen multiple times to the samples. Training was not provided because both raters had experience with administering the CAPE-V. A random selection of 15% of the samples was doubled to calculate the intra-rater reliability. For this study, the CAPE-V overall severity was selected as a primary outcome parameter. The analysis of the other CAPE-V parameters can be found in Appendix I.

C. Psychosocial wellbeing

Pediatric Voice Handicap Index (pVHI). A parent completed the Dutch version of the pVHI, which is a parent-proxy tool to gain insight into the physical, functional and emotional impact of the voice disorder on their child (Veder et al., 2017). The pVHI consists of 23 items which are evaluated using a five-point Likert scale (0: never, 1: almost never, 2: sometimes; 3: almost always; 4: always). Total pVHI scores range from 0 to 92 with a higher score corresponding with a greater psychosocial impact. The same parent was asked to complete the questionnaire pre- and posttherapy.

Statistical analysis plan

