The statistical analysis was performed using IBM SPSS Statistics 28 software (SPSS, Inc. Chicago, IL). The significance level was set at $\alpha = 0.05$. One-way ANOVAs were used to check for statistically significant differences in continuous parameters (e.g., age) between the three study arms. Fisher's exact tests were used for the comparison of categorical parameters (e.g., sex) between the three study arms. Pairwise comparisons with Bonferroni corrections ($\alpha < 0.016$) were performed when a significant difference was found between the groups. The inter- and intra-rater reliability of the CAPE-V overall severity has been examined with two-way mixed ICCs and their 95% confidence intervals, type consistency, single-rating, and interpreted following the classification of Koo and Li (2016) ((ICC > 0.9 'excellent'; $0.9 \ge ICC > 0.75$ 'good'; $0.75 \ge ICC > 0.5$ 'moderate'; ICC ≤ 0.5 'poor'). The effects of voice therapy were evaluated using two complementary approaches.

Firstly, a more traditional group-level analysis was conducted. Linear mixed models were used to compare groups over time on the primary outcome parameters, using the restricted maximum likelihood estimation and unstructured covariance type. Time, group, and time-by-group interaction were specified as fixed factors. A random intercept for participants was included and within-group effects of time were determined using pairwise comparisons. Unstandardized effect sizes were presented in the form of the estimated mean differences and 95% confidence intervals for the outcome variables. For the analysis of the AVQI, only participants in whom the SNR of the pretest and posttest voice samples was greater than or equal to 30 dB were selected (Deliyski et al., 2006).

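### The reliability of the CAPE-V overall severity rating is labelled from a consistency-type ICC, which cannot register a constant shift between raters or between listenings, so the label can be about one band too favourable

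*Combined protocol and SAP*

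**What the plan says.** The Statistical analysis plan states that "The inter- and intra-rater reliability of the CAPE-V overall severity has been examined" with "two-way mixed ICCs and their 95% confidence intervals, type consistency, single-rating". The same specification serves both kinds of reliability. The result is then graded: above 0.9 is excellent, above 0.75 up to 0.9 good, above 0.5 up to 0.75 moderate, and 0.5 or below poor.

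The CAPE-V paragraph under Voice quality and vocal capacities gives the setting:

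- **Role:** "the CAPE-V overall severity was selected as a primary outcome parameter".
- **Scale:** parameters are scored "on a visual-analog scale from 0 to 100, where 0 is considered within normal limits".
- **Rating:** two therapists "independently and blindly rated all the pseudonymized samples in a random order".
- **Consensus:** afterwards "they relistened to the samples together to compare their individual evaluations and to reach a consensus".
- **Training:** "Training was not provided because both raters had experience with administering the CAPE-V".
- **Repeats:** "A random selection of 15% of the samples was doubled to calculate the intra-rater reliability".

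The documents plan no absolute-agreement ICC, mean rater difference or limits of agreement, and they give no reason for preferring consistency.

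**The concern.** A consistency ICC asks whether two sets of scores move together after any constant difference between them has been removed. An absolute-agreement ICC asks whether the scores are the same. If one rater scores every child 10 points higher than the other, the first statistic is untouched and the second falls.

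The gap matters most for intra-rater reliability. There the question is whether one rater gives the same recording the same score twice, and a uniform shift between listenings is a failure to do so. For inter-rater reliability a shift is at least possible: the scale has a fixed, meaningful zero, and the CAPE-V raters were not calibrated together. By contrast, the laryngostroboscopy raters had a half-hour session covering each parameter, although both already knew the VALI form.

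What is at stake is the reliability figure and its label, not the therapy effect. CAPE-V overall severity is left out of the individual-level analysis because no relevant degree of change has been established for it. The ICC is therefore the main evidence of measurement quality that readers will have for this outcome.

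**Working it through.** The documents state no ICC value, SD or number of samples, so there is no figure of the plan's own to reproduce. The check is algebraic, with assumed inputs.

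**Inputs from the documents.** Two raters (or two listenings), a single-rating ICC, and label limits at 0.9, 0.75 and 0.5.

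**Assumed inputs.** Between-sample SD 15 (variance Vs = 225), error SD 6 (variance Ve = 36), and a constant shift of d points.

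**Formulas for two columns of scores.**

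- Consistency: Vs / (Vs + Ve)
- Absolute agreement: Vs / (Vs + Ve + d²/2)

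**Results with error SD 6.**

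- Consistency, any d: 225 / 261 = 0.86, *good*.
- Agreement, d = 5: 225 / (261 + 12.5) = 0.82, still *good*.
- Agreement, d = 10: 225 / (261 + 50) = 0.72, *moderate*.
- Shift at which agreement falls to 0.75: 225 / 0.75 = 300 = 261 + d²/2, so d = √78 = 8.8 points.
- Shift at which agreement falls to 0.5: 225 / 0.5 = 450 = 261 + d²/2, so d = √378 = 19.4 points.

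**Sensitivity to the error SD.** With error SD 8, consistency is 225 / 289 = 0.78. The 0.75 limit is then reached at d = √(2 × (300 − 289)) = 4.7 points. That case starts just above the limit, so a small shift is bound to move the label.

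**Sensitivity in general form.** Let c be the consistency ICC and S the total SD of one rater's scores across samples (S² = Vs + Ve). Agreement is then c·S² / (S² + d²/2), and the shifts that reach the two limits are:

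- to 0.75: S·√(2(c/0.75 − 1))
- to 0.5: S·√(2(2c − 1))

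| c | S | shift to 0.75 (points) | shift to 0.5 (points) |
|---|---|---|---|
| 0.80 | 10 | 3.7 | 11.0 |
| 0.85 | 15 | 7.7 | 17.7 |
| 0.90 | 20 | 12.6 | 25.3 |

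A simulation of 200,000 samples with S = 15 and c = 0.85 confirmed the formulas. The consistency ICC stayed at 0.849 at every shift. The agreement ICC was 0.849, 0.805, 0.695, 0.566 and 0.449 at shifts of 0, 5, 10, 15 and 20 points.

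**Finite samples (Vs = 225, Ve = 36, d = 10).** If 60 samples are assumed for the inter-rater ICC, the consistency estimate exceeds 0.75 in about 99% of simulated studies and the agreement estimate in about 29%. These figures do not carry over to intra-rater reliability: 15% of 60 samples is 9 pairs. With 9 pairs the proportions are about 82% and 40%, and the central 95% of consistency estimates runs from roughly 0.52 to 0.97. At that size imprecision is at least as large a problem as the choice of ICC type.

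**The case against.** The strongest reply is that no planned CAPE-V analysis uses the absolute level of the score. The outcome enters only the mixed model with time, group and their interaction, and the documents state no CAPE-V cut-off between normal and dysphonic voices. Both raters score every sample, so a constant offset between them cancels from pre-post change and from contrasts between arms. For that use an inter-rater consistency ICC is defensible, and the plan discloses its model, type and unit openly. **This stands.** It is why the inter-rater value need not be withdrawn, only accompanied.

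Second, the ICCs describe individual ratings made before consensus, whereas the consensus score appears to be the one analysed. Neither ICC type estimates the reliability of that score. **This also stands**, and it calls for a sentence in the plan.

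Third, drift is not wholly invisible to a consistency ICC. If the repeats are mixed into the random order, the gap between listenings varies and part of the drift becomes error. With the same assumed SDs and a linear drift of 30 points over the session, consistency falls from 0.86 to about 0.81 when the columns are first and second listening. It falls to about 0.67, the same as agreement, when the two listenings are entered in arbitrary order. **This stands in part:** only the uniform component of a shift escapes, but that component does escape.

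Fourth, nothing in the documents shows that a shift occurred, and both raters were experienced. This is true, but the planned statistic could not show one if it had.

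Two stronger readings are tempting and not supported. A reader might infer that the treatment effect on CAPE-V is biased; the blinded, randomly ordered rating of all samples by the same pair argues against that. A reader might also infer that a rating in the plan's *poor* range would be passed off as *good*; under the main assumptions that needs a shift of about 19 points.

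**Conclusion.** The point holds as a limited one. The consistency-type ICC ignores a constant shift, nothing else in the plan would reveal it, and the plan converts the value into a label for a primary outcome. A moderate shift can make that label about one band too favourable. Under the main assumptions it turns *good* into *moderate* at 8.8 points; across consistency ICCs of 0.80 to 0.90 and total SDs of 10 to 20, the threshold ranges from 3.7 to 12.6 points. All SDs, shifts and sample numbers here are assumptions. If there was no shift, the two ICC types coincide and the label is unchanged.

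The case is firm for intra-rater reliability, where the same score should be returned for the same recording. For inter-rater reliability it is weaker, because consistency is a legitimate choice when only contrasts are analysed; the fault is in reading the value as agreement. Severity is minor: a cheap improvement in reporting.

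**What to change.** In the Statistical analysis plan:

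1. Use the absolute-agreement type for the intra-rater ICC.
2. For the inter-rater ICC, report absolute agreement beside the consistency value, both with 95% confidence intervals, and base any label about agreement on the former.
3. Report the mean difference between raters, and between first and second listening for each rater, in scale points with 95% confidence intervals.
4. State that these ICCs describe individual ratings before consensus and not the consensus score, and say which score enters the mixed model.

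The cost is one software option and a few lines of text, using ratings already collected. The reported ICC and its label may come out less favourable. The intra-rater estimate will remain imprecise whichever type is used, because only 15% of the samples were repeated, so its interval should be read along with its label.

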Effect of Semi-occluded Vocal Tract Therapy on the Phonation of Children With Vocal Fold Nodules

NCT05878197

22/05/2024

Study protocol

This study was approved by the Ethics Committee of Ghent University Hospital (registration number: B670201936069) and has been registered on ClinicalTrials.gov. The consolidated standards of reporting trials (CONSORT) non-pharmacologic treatment interventions (NPT) checklist were used to report the trial specifications (Boutron et al., 2017). Written informed consent was obtained from a parent of each participant.

Participants

Children between six and 12 years old (primary school) with VFNs were eligible to participate in this study. Participants were recruited between October 2019 and January 2023 during their consultations at the voice unit of Ghent University Hospital, through flyers in other hospital departments, through social media, or by referral from voice therapists who were informed about this project. All participants were diagnosed with VFNs by an otorhinolarygologist with extensive experience in voice diagnostics ([name]). This age group was chosen because these children can cooperate with voice therapy and tolerate videolaryngostroboscopy. Exclusion criteria were a history of phonosurgery, nasal or ear diseases, neurological disorders, and parent-reported pubertal voice changes.

Design

A randomized controlled study design was used. Participants were assigned to one of the three study arms (experimental group "SP", experimental group "RVT", or the control group (CG) receiving indirect treatment), depending on their time of registration. The order in which the different voice treatments were organized was determined using a random number list. No changes in the methodology were made after trial commencement.

Voice therapy

In each study arm, a short-term, intensive, group therapy program was provided. All participants received 11 hours of voice therapy spread over four consecutive days (three hours on day 1-3 and two hours on day 4). Each group consisted of a minimum of two and a maximum of five children and was guided by one experienced voice therapist ([name] or [name]). All therapy sessions were provided at Ghent University Hospital. During the study period, participants were not allowed to attend external voice therapy.

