The content and hierarchical structure of the different study arms were kept as similar as possible, with the exception of the direct vocal techniques. In the CG, no direct technique was included. Offered therapy consisted of basic education of the vocal mechanism, normal vocal function, and VFNs, vocal hygiene recommendations, posture advice, and costo-abdominal breathing exercises. Participants in the experimental groups received the same counseling and breathing exercises, combined with the direct vocal technique

SP or RVT. For SP, participants used a stainless-steel drinking straw with a diameter of 5 mm and a length of 23 cm. In each study arm, vocal rest pauses and play activities (identical for the experimental groups) were provided. Since no direct vocal technique was practiced in the CG, more play activities were scheduled in which excessive or loud voice use was being monitored and limited. Home exercises were foreseen in each study arm. Parents were not present during therapy but were informed verbally and in writing about the content of the therapy sessions so they could supervise home exercises.

Voice assessment

A standardized and multidimensional voice assessment, based on the protocol of the European Laryngological Society (Dejonckere et al., 2003) and supplemented with the acoustic voice quality index (AVQI) (Maryn et al., 2010a), was performed one day before the start of voice therapy and immediately after the last voice therapy session. A standardized pretest anamnesis by means of a semi-structured interview (see Appendix H) was used to examine the demographic characteristics, therapy history, vocal complaints, and risk factors. The assessments were performed by eight voice therapists of the Center for Speech and Language Sciences ([name], [name], [name], [name], [name], [name], [name], and [name]) with experience in voice diagnostics in two acoustically treated rooms at Ghent University Hospital. The assessors were blinded to group allocation and participants were assessed by the same assessor pre- and posttherapy. Voice assessment consisted of the following parts: (a) laryngeal anatomy and function, (b) voice quality and vocal capacities, and c) psychosocial wellbeing.

A. Laryngeal anatomy and function

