The Acoustic Voice Quality Index (AVQI) is an objective, multiparameter approach to quantify dysphonia severity on the basis of a sustained vowel [a:] and continuous speech (Maryn et al., 2010a). The index consists of a weighted combination of six time-domain parameters [i.e., shimmer local (SL), shimmer local decibels (SLdB), and harmonics-to-noise ratio (HNR)), frequency-domain parameters (i.e., general slope of the spectrum (slope) and tilt of the regression line through the spectrum (tilt)), and quefrency-domain parameters (i.e., smoothed cepstral peak prominence (CPPs)]. The formula of the AVQI is 2.571 (3.295 - 0.111 CPPs - 0.073 HNR - 0.213 SL + 2.789 SLdB - 0.032 slope + 0.077 tilt). The index ranges from 0 to 10 and a higher index indicates poorer voice quality. The threshold score that distinguishes a normophonic voice from a dysphonic voice in Dutch

adults is 2.95 (Maryn et al., 2010a). An Australian study suggested a threshold score of 3.46 in the pediatric population, but norm values for Dutch children are missing (Reynolds et al., 2012). In order to calculate the AVQI, the participants were asked to produce a sustained vowel [a:] at normal pitch and loudness and to read the Dutch phonetically balanced text "Papa and Marloes" (Van de Weijer & Slis, 1991). A Samson C01U Pro microphone, located at a distance of 15 cm from the mouth, and the software program PRAAT were used (Boersma & Weenink). A midvowel segment of 3 seconds of the vowel [a:] and the first two sentences of the text were combined in an automated script to calculate the AVQI. It is known that a minimum signal-to-noise ratio (SNR) of 30 dB is required to obtain acceptable perturbation measurements (Deliyski et al., 2005). For this reason, all participants with a pre- or posttest sample with an SNR less than 30 dB were removed from the analyses of the AVQI.

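### The between-arm comparison is a change-score contrast that ignores the pretest as a covariate: valid under randomisation, but usually less precise than a baseline-adjusted estimate

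*Combined protocol and SAP*

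**What the plan says.** The Voice assessment section gives two time points; the assessment "was performed one day before the start of voice therapy and immediately after the last voice therapy session". In the Statistical analysis plan, the group-level analysis reads: "Linear mixed models were used to compare groups over time on the primary outcome parameters, using the restricted maximum likelihood estimation and unstructured covariance type". The fixed part of the model is given in full: "Time, group, and time-by-group interaction were specified as fixed factors". The rest of the specification is: "A random intercept for participants was included and within-group effects of time were determined using pairwise comparisons".

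The pretest therefore enters as one of two modelled responses. It is not a covariate, and nothing constrains the pretest means to be equal across arms. One-way ANOVAs and Fisher's exact tests compare the arms on participant characteristics, but nothing from them is carried into the outcome model.

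For AVQI the analysis set consists of complete pairs, because "all participants with a pre- or posttest sample with an SNR less than 30 dB were removed from the analyses of the AVQI". For DSI, CAPE-V overall severity and pVHI the documents do not say whether pairs are complete.

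On allocation, the Design section assigns arms according to time of registration and adds: "The order in which the different voice treatments were organized was determined using a random number list".

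**The concern.** With one pretest and one posttest, the time-by-group term compares mean change between arms. That amounts to fixing the coefficient on the pretest at 1. Under randomisation with equal pre and post SDs, the most efficient coefficient is the pre/post correlation, rho, which is below 1. Two things follow.

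- **Precision.** The confidence interval for the arm effect is usually wider than these data need give. That matters most if the arms are small.
- **Chance imbalance.** If two arms differ at pretest by chance, the change-score estimate moves in the opposite direction, because regression to the mean is counted as treatment effect. Averaged over randomisations this cancels; in the one trial that was run it does not.

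This is not a claim of bias in the planned model.

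**Working it through.** The plan states no sample size, SD, correlation or power figure, so there is nothing of its own to reproduce.

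**Inputs.** From the documents: three arms, two time points, the fixed terms and the random intercept. Assumed: equal pre and post SDs (relaxed in step 4), three equal arms of n (N = 3n), rho from 0.5 to 0.9, and independent children.

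**1. Equivalence.** A REML random-intercept model with time, group and time-by-group was fitted to simulated complete pairs, 3 arms of 12. The interaction estimates were 0.4717 and 0.3726, each with SE 0.3153. The plain differences in mean change and their SE were identical. ANCOVA on the same data gave SEs of 0.243 and 0.244. With missing posttests the identity is approximate.

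**2. Variance.** In units of the outcome variance:

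- change score: proportional to 2(1 − rho)
- ANCOVA: proportional to (1 − rho²) × (1 + 1/(N − 5)), where the last factor is the average cost of estimating the slope
- ratio, adjusted to planned: (1 + rho)/2 × (1 + 1/(N − 5))

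For n = 10 and rho = 0.5: 0.75 × (1 + 1/25) = 0.78.

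| n per arm | rho 0.5 | 0.7 | 0.8 | 0.9 | break-even rho |
|---|---|---|---|---|---|
| 5 | 0.83 | 0.94 | 0.99 | 1.05 | 0.82 |
| 10 | 0.78 | 0.88 | 0.94 | 0.99 | 0.92 |
| 15 | 0.77 | 0.87 | 0.92 | 0.97 | 0.95 |

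Break-even is where the ratio equals 1: rho = 2(N − 5)/(N − 4) − 1. For n = 10 this is 50/26 − 1 = 0.92; for n = 8 it is 38/20 − 1 = 0.90. Above it, adjustment loses slightly.

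**3. What the ratios mean at n = 10.** The SE falls by 1 − √ratio: 12%, 6%, 3% and 0.6%. The equivalent gain in children is 1/ratio − 1: 28%, 13%, 7% and 1%. Simulation with 40,000 trials per cell gave variance ratios of 0.78, 0.89, 0.93 and 0.99 for ANCOVA, and 0.79, 0.88, 0.94 and 0.99 for the common-baseline model. Coverage was about 95% and mean error about zero for the planned and adjusted estimators.

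**4. Unequal SDs.** With k = SDpost/SDpre, the ratio is (1 − rho²)k²/(1 + k² − 2·rho·k) × (1 + 1/(N − 5)). At n = 10 and rho 0.5, 0.7, 0.8, 0.9:

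- k = 1.1: 0.85, 0.96, 1.01, 1.04
- k = 0.9: 0.69, 0.78, 0.82, 0.84

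**5. Baseline imbalance.** Given an observed pretest difference D between two arms, the expected change-score contrast shifts by −(1 − rho)D. For D = 0.5 SD the shift is 0.25, 0.15, 0.10 or 0.05 SD in size at rho 0.5, 0.7, 0.8 or 0.9. At n = 10, D has standard deviation √(2/10) = 0.45 SD, so the absolute difference exceeds 0.5 SD for a given pair of arms in 26% of randomisations.

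**6. Therapy groups.** Children were treated in groups of two to five, so independence is doubtful. With 12 per arm in three groups of four and an assumed posttest intraclass correlation of 0.10, simulation gave ratios of 0.81 to 0.84, 0.90 to 0.93, 0.94 to 0.97 and 0.98 to 1.00 at rho 0.5, 0.7, 0.8 and 0.9. The spread reflects how the group effect enters the posttest variance. Without clustering the formula gives 0.77, 0.88, 0.93 and 0.98.

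**The case against.** The planned model is a conventional and valid pre/post analysis, so the choice is between two acceptable estimators. That is right, and it limits the weight of the point.

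No input to the magnitude comes from the documents, and the two assessments are only days apart, so a high correlation cannot be excluded. At 0.9 there is almost nothing to gain. This stands, and it is why a range is shown.

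Clustering shrinks the gain. It does, as step 6 shows: the figures for extra children are upper values, and an arm of five could be a single therapy group, so that row is only indicative. In the case simulated, the direction does not reverse.

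Baseline adjustment leans on exchangeable arms, while children were assigned by time of registration. If arms differ systematically by registration period, a change score removes stable differences that ANCOVA or a common-baseline model would not fully remove, and neither method is clearly better. This is a real condition on the remedy, and a reason to show both estimates.

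Finally, the plan names only within-group pairwise comparisons and does not spell out which between-arm intervals will be reported. But it gives comparing groups over time as the purpose of the model, and the interaction is the only term that does so.

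**Conclusion.** The point holds as one of efficiency. With complete pairs, the planned arm comparison is the difference in mean change. It is unbiased if the treatment order was truly random, and it is usually less precise than an estimate adjusted for a pretest already collected. With about 10 per arm, the SE reduction is modest to useful at correlations up to about 0.8 and negligible at 0.9. There is a small loss above the break-even correlation, in very small arms, or when the posttest SD is larger and the correlation high. The sizes depend on assumed arm sizes, SDs, correlation and independence of children. The effect of therapy groups on the standard errors is a separate question that baseline adjustment does not settle.

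**What to change.** For each outcome, add an arm effect adjusted for the pretest, with its 95% confidence interval. Either form will do:

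- ANCOVA of the posttest on arm and pretest; or
- the longitudinal model with a common baseline mean, which also keeps the planned within-group time effects. Code the arm effect as two indicators, post × SP and post × RVT, alongside time. Deleting the group main effect while time and the interaction remain as factors does not work: it still fits all six time-by-arm means (design rank 6, against 4 with the indicators) and leaves the estimate unchanged.

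The plan is written in the past tense. If results are already known, report the adjusted estimate beside the planned model and label it post hoc. State how the random order governed allocation, since both forms rely on it.

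The cost is one further analysis per outcome on existing data and about one degree of freedom for the slope, with little or no gain at a correlation of 0.9 and a slight loss in very small arms.

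### Every arm is delivered in therapy groups of 2 to 5 children, but the analysis has no therapy-group term, so precision is overstated if change is correlated within groups

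*Combined protocol and SAP*

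**What the plan says.** **Delivery (Voice therapy section).** "In each study arm, a short-term, intensive, group therapy program was provided", control arm included. "Each group consisted of a minimum of two and a maximum of five children and was guided by one experienced voice therapist". "All participants received 11 hours of voice therapy spread over four consecutive days".

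**Allocation (Design section).** Children entered an arm "depending on their time of registration". What was randomised is described as follows: "The order in which the different voice treatments were organized was determined using a random number list". This reads as if arms were attached to blocks of sessions and not to individual children, but the documents do not say so outright. They also do not give the number of allocated units or therapy groups per arm.

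**Analysis (Statistical analysis plan).** The group-level model has fixed effects for time, study arm and their interaction. The word group there means study arm, not therapy group. The random part is "A random intercept for participants was included". From the same model, "within-group effects of time were determined using pairwise comparisons". The individual-level analysis puts Wilson 95% intervals around the proportions improved, unchanged and deteriorated. No therapy-group or therapist effect, robust variance or sensitivity analysis for clustering appears anywhere.

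**The concern.** Children who spend four days together with one therapist share that therapist's delivery, the group's dynamics and the events of those days. Their changes may therefore be correlated. The planned analysis treats them as independent.

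This does not depend on how the allocation text is read. If whole sessions were allocated, the trial is cluster-allocated and the unit of analysis is wrong. If children were allocated individually, their outcomes are still clustered by delivery.

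With a positive correlation, standard errors and p-values are too small on the comparisons that carry the trial's conclusions. The trial could then report an arm difference, or a within-arm benefit, that reflects how a few therapy groups happened to go.

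**Working it through.** The plan gives no sample size, variance, ICC or number of therapy groups, so it has no figure of its own to reproduce.

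**Inputs from the documents:** therapy-group size m from 2 to 5; three arms; significance level 0.05 (taken as two-sided, since the plan does not say).

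**Assumed inputs:** ICC of pre-post change from 0 to 0.20; 3, 5 or 8 therapy groups per arm.

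**Step 1: what the model can capture.** Write the change of child i in therapy group j as d_ij = arm effect + g_j + e_ij, with ICC = var(g) / [var(g) + var(e)]. A participant intercept enters both the pre and the post score, so it cancels from d_ij. The planned model therefore sets var(g) to zero. The unstructured covariance type does not change this, because participant is the only subject named. A therapy-group intercept would cancel in the same way. The missing term is therapy group by time.

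**Step 2: standard errors.** Design effect DE = 1 + (m − 1) × ICC. The true SE divided by the planned SE is √DE.

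| m | ICC 0.05 | ICC 0.10 | ICC 0.20 |
|---|---|---|---|
| 2 | DE 1.05, SE ×1.02 | DE 1.10, SE ×1.05 | DE 1.20, SE ×1.10 |
| 3.5 | DE 1.125, SE ×1.06 | DE 1.25, SE ×1.12 | DE 1.50, SE ×1.22 |
| 5 | DE 1.20, SE ×1.10 | DE 1.40, SE ×1.18 | DE 1.80, SE ×1.34 |

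For a single contrast, the actual two-sided level is about 2 × [1 − Φ(1.96 / √DE)]. At m = 3.5 this gives 0.065, 0.080 and 0.110. At ICC 0.01 it is 0.051 to 0.055 for m from 2 to 5, which is negligible.

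**Step 3: simulated type I error.** Null trials were simulated and tested with a one-way F test on child-level change. With complete pre-post pairs, this matches the time-by-arm test of the stated model. There were 12,000 trials per cell (8,000 for the within-arm row).

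| Test and layout | ICC 0.05 | ICC 0.10 | ICC 0.20 |
|---|---|---|---|
| Three-arm test, sizes mixed 2–5 | 7% | 9–10% | 15% |
| Three-arm test, all groups of 2, 5 per arm | 6% | 7% | 9% |
| Three-arm test, all groups of 5, 5 per arm | 8% | 12% | 20% |
| Within-arm change, 5 groups of 2–5 | 6% | 8% | 11% |

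At ICC 0 the three-arm test is at about 5%. The mixed-size results are nearly the same with 3, 5 or 8 therapy groups per arm, so they do not hinge on that unstated number. A test on therapy-group mean changes held 4.5–5.4%.

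**Step 4: if allocated blocks held more than one therapy group.** With an assumed 3 blocks of 2 therapy groups per arm and the shared variation at block level, the child-level test rejects in 10%, 16% and 28% of null trials at ICC 0.05, 0.10 and 0.20. Therapy-group means still reject in 7%, 9% and 14%. Block means reject in about 5%. The unit of allocation therefore decides the level at which to cluster.

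**Step 5: proportion intervals.** For illustration, assume 40% improved and n = 18, and replace n by n / DE in the Wilson formula. The interval is 21–62% if children are independent, 21–63% at DE 1.05, 20–65% at DE 1.25 and 17–69% at DE 1.80.

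**The case against.** The strongest reply is that every figure above the nominal level rests on an ICC that the documents do not supply, and the ICC could be low. Content and structure were kept as similar as possible across arms. "The assessors were blinded to group allocation", and each child had the same assessor before and after therapy. CAPE-V samples were rated blind in random order. The pVHI is completed by parents, who were not present at sessions. The ICC may also differ by outcome. The largest figures need every group to have five children and an ICC of 0.20. For AVQI, the signal-to-noise exclusion can make the analysed groups smaller. The Wilson example is invented (40% of 18 is not a whole number of children), and its interval hardly moves at a middle design effect.

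The remedy also has weaknesses. With few therapy groups, the group variance is poorly estimated. In a check at ICC 0.05, REML set it to exactly zero in 45%, 41% and 35% of trials with 3, 5 and 8 groups per arm. The group-means analysis loses power. At ICC 0, with an assumed 0.8 SD benefit in both active arms, power falls from 40% to 26% with 3 groups per arm and from 66% to 51% with 5.

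Most of these facts stand, and they limit what can be said about size. They do not remove the problem. Blinded assessment limits shared measurement error, not shared response to the same sessions. The plan assumes an ICC of zero without saying so or checking it. The unstable variance estimate did not make the corrected test invalid: a simple version of it, using between-group degrees of freedom when the estimated variance was nonzero, kept type I error at 2–6%.

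**Conclusion.** The concern holds. The analysis omits the level at which therapy was delivered, and nothing else in the plan compensates. For the documented group sizes and an assumed ICC of change of 0.05 to 0.20, true standard errors are about 2.5% to 34% larger than those the model reports. With mixed group sizes, type I error of the three-arm test is about 7% to 15% against a nominal 5%. At ICC 0 there is no inflation, at 0.01 it is negligible, and a negative correlation would act in the opposite direction. It is certain that the term is missing; how far the p-values are off is unknown. The effect on the Wilson intervals is the smaller part. The time-by-arm and within-arm tests should be corrected before they are relied on.

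**What to change.** 1. Add a random therapy-group-by-time effect to each mixed model, with Satterthwaite or Kenward-Roger degrees of freedom. Keep it whether or not it is significant.
2. As a check suited to few groups, compare arms on therapy-group mean changes, and acknowledge the loss of power.
3. A baseline-adjusted model of the post-therapy score with a therapy-group random intercept is an alternative, but it has a different estimand and should not be presented as equivalent.
4. Label the Wilson intervals as assuming independent children, or widen them over a stated ICC range.
5. State the unit of allocation, and the number of allocated units and therapy groups per arm. If a block held several therapy groups, cluster at block level.
6. Add therapist as a covariate only if both therapists led groups in every arm, which the Voice therapy section does not say.

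**Cost.** This is a re-analysis of existing data. It should be reported as post hoc, because recruitment ended in January 2023 and the plan describes the analysis in the past tense. It needs therapy-group membership from session records, and the documents do not say that an identifier was kept. If membership cannot be recovered, the report should state the independence assumption and show results over a range of ICC values. With a positive correlation, intervals will be wider, and the therapy-group variance will be imprecise if groups are few.
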